2.2.1 Randomization and drug dispensing irregularities

Randomization and drug-dispensing irregularities occur whenever:

1. A randomization is not in accordance with the protocol-defined randomization method, such as a) an ineligible patient is randomized, b) a patient is randomized based on an incorrect stratum, or c) a patient is randomized twice.

OR

2. A patient is dispensed an IMP kit not allocated by the protocol-defined randomization, such as a) a patient at any time in the study is dispensed a different treatment kit than as

randomized (which may or may not contain the correct-as-randomized IMP), or b) a non-randomized patient is treated with IMP reserved for randomized patients.

Randomization and drug-dispensing irregularities will be monitored throughout the study and reviewed on an ongoing basis.

All randomization and drug-dispensing irregularities will be documented in the clinical study report. If the number of irregularities is large enough to make a tabular summary useful, the irregularities will be categorized and summarized among randomized patients (number and percentages).

Randomization and drug-dispensing irregularities to be prospectively identified include but are not limited to:

Randomization and drug allocation irregularities
Kit dispensation without IRT transaction
Erroneous kit dispensation
Kit not available
Randomization by error
Patient randomized twice
Stratification error
Patient switched to another site

2.3 ANALYSIS POPULATIONS

The randomized population includes any patient who has signed informed consent and has been allocated to a randomized treatment regardless of whether the treatment kit was used.

For any patient randomized more than once, only the data associated with the first randomization will be used in any analysis population. The safety experience associated with any later randomization will be assessed separately.

2.3.1 Efficacy populations

The primary efficacy analysis population will be the mITT population.

2.3.1.1 *Modified intent-to-treat (mITT) population*

The mITT population includes all randomized patients who have received at least one dose of investigational product analyzed according to the treatment group allocated by randomization.

Randomized patients for whom it is unclear whether they took the study medication will be included in the mITT population.

2.3.2 Safety population

The safety population is defined as all patients exposed to IMP, regardless of the amount of exposure, analyzed according to the treatment actually received.

In addition:

- Randomized patients for whom it is unclear whether they took the IMP will be included in the safety population as randomized
- The actual treatment group will be the one for which the patient received the majority of doses.

2.3.3 Pharmacokinetic analysis population

The PK population will consist of all patients in the safety population with at least one post-dose, non-missing serum SAR440340 or serum dupilumab concentration. Patients will be analyzed according to the treatment actually received.

2.3.4 Anti-drug antibody population

The ADA population will consist of all patients who received any study drug and who had at least one non-missing ADA result in the anti-SAR440340 or anti-dupilumab assay after first dose of the study drug. Patients will be analyzed according to the treatment actually received.

2.4 STATISTICAL METHODS

2.4.1 Demographics and baseline characteristics

Continuous data will be summarized using the number of available data, mean, standard deviation (SD), median, Q1, Q3, minimum and maximum for each treatment group. Categorical and ordinal data will be summarized using the number and percentage of patients in each treatment group.

Parameters will be summarized on the randomized population analyzed in the treatment group to which they were randomized. Parameters described in [Section 2.1.1](#) will be summarized by treatment group and overall treatment groups using descriptive statistics.

Medical and surgical history will be summarized by treatment group and by primary system organ class (SOC) and preferred term (PT) sorted by internationally agreed order of SOC and by the decreasing frequency of PT within SOC based on the overall incidence across treatment groups. Atopic medical history will be summarized separately.

No statistical testing on demographic and baseline characteristic data will be performed.

No specific description of the safety parameters will be provided at baseline. If relevant, the baseline values will be described along with each safety analysis.

2.4.2 Prior or concomitant medications

The prior and concomitant medications will be presented for the mITT population.

Medications will be summarized by treatment group according to the WHO-DD dictionary, considering the first digit of the Anatomic Therapeutic Class (ATC) (anatomic category) and the first 3 digits of the ATC class (therapeutic category). All ATC codes corresponding to a medication will be summarized, and patients will be counted once in each ATC category (anatomic or therapeutic) linked to the medication. Therefore patients may be counted several times for the same medication.

The table for prior medications will be sorted by decreasing frequency of anatomic class followed by decreasing frequency of therapeutic classes within anatomic class based on the overall incidence across treatment groups. In case of equal frequency regarding ATCs (anatomic or therapeutic categories), alphabetical order will be used.

Concomitant medications will be summarized for the treatment epoch and treatment emergent period separately. The tables for concomitant medications will be sorted by decreasing frequency of anatomic class followed by decreasing frequency of therapeutic classes within anatomic class based on the incidence in the SAR440340 and dupilumab coadministration group. In case of equal frequency regarding ATCs (anatomic or therapeutic categories), alphabetical order will be used.

2.4.2.1 *Background therapy*

Pre-screening ICS/LABA background therapy will be summarized by treatment group sorted by decreasing frequency of standard medication name on the incidence in the overall treatment group.

During the screening and randomized IMP treatment periods, the daily intake of the study-specific background therapy will be recorded in the electronic diary. Compliance rate for the study-specific background therapy will be calculated for each patient. For each day, a patient is considered as compliant if the actual dose taken is the same as or greater than the prescribed dose recorded on the eCRF. Compliance rate is defined as the number of days when the patient is compliant divided by the number of days the patient stays in the background therapy stabilization phase and the background therapy withdrawal phase.

2.4.3 Extent of investigational medicinal product exposure and compliance

The overall extent of IMP exposure and compliance will be assessed and summarized by actual treatment within the safety population ([Section 2.3.2](#)).

2.4.3.1 *Extent of investigational medicinal product exposure*

The extent of IMP exposure will be assessed by the duration of IMP exposure.

Duration of IMP exposure is defined as last dose date – first dose date + 14 days, regardless of unplanned intermittent discontinuations (see [Section 2.5.3](#) for calculation in case of missing or incomplete data).

Duration of IMP exposure will be summarized descriptively as a quantitative variable (number, mean, SD, median, Q1, Q3, minimum, and maximum). In addition, duration of treatment exposure will also be summarized categorically by numbers and percentages of patients in each of the following categories and cumulatively according to these categories:

- >0 and \leq 2 weeks
- >2 and \leq 4 weeks
- >4 and \leq 8 weeks
- >8 weeks and < 12 weeks – 3 days
- \geq 12 weeks – 3 days

Additionally, the cumulative duration of treatment exposure will be provided, defined as the sum of the duration of treatment exposure for all patients, and will be expressed in patient years.

2.4.3.2 Compliance

A given administration will be considered non-compliant if the patient did not take the planned dose of treatment as required by the protocol. No imputation will be made for patients with missing or incomplete data.

Percentage of compliance for a patient will be defined as the number of administrations that the patient was compliant divided by the total number of administrations that the patient was planned to take during the treatment epoch defined in [Section 2.1.4](#).

Treatment compliance will be summarized descriptively as quantitative variables (number, mean, SD, median, Q1, Q3, minimum, and maximum). The percentage of patients whose compliance is <80% will be summarized. In addition, numbers and percentages of patients with an overdose will be summarized.

Cases of overdose (defined as at least twice the intended dose during an interval of less than 8 days) will be listed as such. More generally, dosing irregularities are listed in [Section 2.2.1](#).

2.4.4 Analyses of efficacy endpoints

All efficacy endpoints will be analyzed using the mITT population. [Table 4](#) summarizes the pairwise comparisons to be conducted in accordance with study objectives. Each comparison on each endpoint will be tested at a two-sided 5% significance level.

Table 4 - Pairwise comparisons and study objectives

	Primary endpoint	Secondary endpoints	Other efficacy endpoints
SAR440340 vs. placebo	P	S	O
Coadministration of SAR440340 and dupilumab vs. placebo	P	S	O
Coadministration of SAR440340 and dupilumab vs. SAR440340	O	S	O
Coadministration of SAR440340 and dupilumab vs. dupilumab	O	S	O
Dupilumab vs. placebo (as calibrator only)	O	O	O

P: Primary objective; S: Secondary objective; O: Other objective

2.4.4.1 Analysis of primary efficacy endpoint(s)**Main statistical model and adjustment of covariates**

The primary endpoint of incidence of LOAC will be analyzed using a logistic regression model. The model will include terms for treatment, baseline eosinophil strata, region (pooled countries), background ICS dose level at randomization and number of exacerbation events within 1 year prior to screening.

For each pairwise treatment comparison, the odds ratio, and corresponding 95% confidence interval (CI) and two-sided p-value will be derived from this model. Sample SAS code is provided below:

```
proc genmod data=loacdata descending;
  class trt01pn eosbgp1n cntygr1 icsgrp;
  model resp = trt01pn eosbgp1n cntygr1 icsgrp asmanum /dist=bin
link=logit type3;
  estimate "SAR440340 vs Placebo"      trt01pn -1 1 0 0 / exp;
  estimate "Coadministration vs Placebo" trt01pn -1 0 1 0 / exp;
  estimate "Coadministration vs SAR440340" trt01pn 0 -1 1 0 / exp;
  estimate "Coadministration vs Dupilumab" trt01pn 0 0 1 -1 / exp;
  estimate "Dupilumab vs Placebo"        trt01pn -1 0 0 1 / exp;
  ods output Estimates = Estimates;
run;
```

All reported LOAC events will undergo the standard medical review process to ensure the events are in-line with the protocol definition. For patients discontinued due to a reason other than LOAC, but for which LOAC could be suspected, the case will be medically reviewed, with appropriate queries sent to the respective site, for final determination of LOAC status to be recorded in the clinical database prior to database lock. As such, there should not be missing data for the primary LOAC endpoint.

Supportive analysis

- *Supportive analysis 1:* Relative risk and corresponding 95% CI for each pairwise treatment comparison will be estimated from a log-binomial regression model. The covariates to be included will be the same as those in the main model.
- *Supportive analysis 2:* Time to LOAC post-randomization, defined as (onset date of LOAC – randomization date + 1), will be analyzed using a Cox regression model. The model will include treatment, baseline eosinophil strata, region, background ICS dose level at randomization and number of exacerbation events within 1 year prior to screening as covariates. A patient without experiencing the event of interest will be considered as censored at date of EOT/Week 12 or the last contact date, whichever occurs earlier. Hazard ratio and corresponding 95% CI and p-value will be estimated for each pairwise treatment comparison. The Kaplan-Meier (K-M) method will be used to estimate the probabilities of the event at Weeks 4, 8 and 12 for each treatment group. K-M curves will be generated; quartiles and point probabilities will be calculated. Interval estimates will be calculated using 95% point wise CIs. P-value from log-rank test stratified by baseline eosinophil strata and region will also be provided for each pairwise treatment comparison.

Below is sample SAS code for the Cox regression model:

```
proc phreg data=ttevent;
  class trt01pn eosbgp1n cntygrp1 icsgrp / param = glm;
  model aval*cnsr(1) = trt01pn eosbgp1n cntygrp1 icsgrp asmanum;
  estimate "SAR440340 vs Placebo"      trt01pn -1 1 0 0 / exp;
  estimate "Coadministration vs Placebo"  trt01pn -1 0 1 0 / exp;
  estimate "Coadministration vs SAR440340" trt01pn 0 -1 1 0 / exp;
  estimate "Coadministration vs Dupilumab"  trt01pn 0 0 1 -1 / exp;
  estimate "Dupilumab vs Placebo"        trt01pn -1 0 0 1 / exp;
  ods output Estimates = Estimates;
  run;
```

Subgroup analysis

To assess the consistency of treatment effects across the subgroup levels, subgroup analyses will be performed by:

- Age group 1 (<45, \geq 45 years)
- Age group 2 (<65, \geq 65 years)
- Gender (Male, Female)
- Region (East Europe: Poland, Russia, Turkey and Ukraine; Latin America: Argentina, Chile and Mexico; North America: USA)
- Race (White, the others)
- Baseline blood eosinophil strata (<150/mm³, \geq 150 – <300/mm³, \geq 300/mm³)
- Background ICS dose level at randomization (medium, high)
- Baseline FEV1 (< median, \geq median)

- ACQ-5 ($\leq 2, >2$)
- Number of asthma exacerbation prior to the study as defined in [Section 2.1.1](#) ($\leq 1, >1$)
- Baseline weight ($<60, \geq 60 - <100, \geq 100$ kg)
- BMI ($<25, \geq 25 - <30, \geq 30$ kg/m²)
- Smoking history (Former, Never)
- Atopic medical condition (Yes, No)
- Age at onset of asthma ($<12, \geq 12 - <18, \geq 18 - 40, \geq 40$ years)
- Baseline predicted FEV1% ($<$ median, \geq median)
- Baseline periostin (NG/ML) ($<$ median, \geq median)
- Baseline FeNO ($< 25, \geq 25 - < 50, \geq 50$ ppb)

Within each subgroup, descriptive statistics including number of patients and incidence of LOAC will be provided by treatment group. Odds ratio and the corresponding 95% CI for each pairwise comparison will be derived.

Treatment-by-subgroup interaction and its p-value will be derived by a logistic regression model. The model will include treatment, baseline eosinophil strata, region, baseline background ICS dose level, number of exacerbation events within 1 year prior to screening, subgroup (if different from the aforementioned covariates), and subgroup-by-treatment interaction.

2.4.4.2 Analyses of secondary efficacy endpoints

Main statistical model and adjustment of covariates

Change from baseline in pre- and post-BD FEV1 at Week 12 will be analyzed using a mixed-effect model with repeated measures (MMRM) approach. The analysis model will include change from baseline values up to week 12 as response variable and treatment, gender, baseline height, baseline eosinophil strata, region (pooled countries), background ICS dose level at randomization, visit, treatment-by-visit interaction, baseline value and baseline-by-visit interaction as covariates.

Given the potential effects on FEV1 and the goal to obtain as precise a treatment effect estimate as possible, FEV1 values after a LOAC event or initiation of rescue medication will not be included for primary assessment of the secondary endpoints. Inclusion of change from baseline in FEV1 values in the model will follow the rules in Table 5. Data not included in the analysis according to these rules will be set to missing. No imputation will be made for other missing FEV1 measurements.

Table 5 – Data inclusion rules for analyses of secondary and other efficacy endpoints

If the patient has	Use data up to
LOAC with rescue medication ^a	last value before start of LOAC
LOAC without rescue medication ^b	value collected at EOT
OCS use without LOAC	last value before start of OCS
neither LOAC or OCS	value collected at Week 12/EOT

^a If the patient meets at least one of the following three criteria:
- ≥6 additional reliever puffs of salbutamol/albuterol or levosalbutamol/levalbuterol in a 24 hour period (compared to baseline) on 2 consecutive days
- Increase in ICS ≥4 times the last prescribed ICS dose (or ≥50% of the prescribed ICS dose at V2 if background therapy withdrawal completed)
- Requiring use of systemic (oral and/or parenteral) steroid treatment

^b If the patient meets none of the three criteria listed above and meets one or both of the following:
- A 30% or greater reduction from baseline in morning PEF on 2 consecutive days
- Requiring Hospitalization or emergency room visit

The repeated measures analysis will be based on the restricted maximum likelihood method assuming an unstructured covariance to model the within-subject errors. A Kenward-Roger approximation will be used for the denominator degree of freedom. Descriptive statistics including number of patients, mean, standard error, and least squares (LS) means will be provided for each treatment group. Difference in LS means and the corresponding two-sided 95% CI and p-value will be provided for each pairwise treatment comparison. Sample SAS code can be found below:

```

proc mixed data=fev1data method=reml;
  class usubjid trt01pn sex cntygr1 eosbgp1n icsgrp avisitn;
  model chg = trt01pn sex hgtbl cntygr1 eosbgp1n icsgrp avisitn
    trt01pn*avisitn base base*avisitn /ddfm=kr residual;
  repeated avisitn / subject=usubjid type=un;
  lsmeans trt01pn*avisitn / pdiff cl;
  ods output LSMeans=LSMeans Diffs=Diffs;
run;

```

If the above model fails to converge, the specification may be changed as follows: 1) use maximum likelihood estimation instead of restricted maximum likelihood method; 2) specify a different covariance structure to reduce the number of unknown parameters to be estimated, the path will be UN→TOEPH→TOEP→AR(1).

Sensitivity analysis

The following sensitivity analyses will be conducted to assess the robustness of the main model:

Analyses using the same MMRM model and estimation methods as specified above:

- *Sensitivity analysis 1:* Inclusion of all FEV1 measurements collected up to EOT for all patients. Missing data will not be imputed.
- *Sensitivity analysis 2: Per protocol analysis*

Exclusion of post-baseline FEV1 measurements in patients (and within time windows) where the patient had a protocol deviation considered to have a potential impact on efficacy, ie, (1) intake of a prohibited medication(s); (2) IMP and/or required background therapy non-compliance; (3) entry criteria violation. Deviations will be medically/clinically reviewed during the study, with final classification made and recorded prior to database lock. Missing data will not be imputed.

Analyses with imputation for missing FEV1:

- *Sensitivity analysis 3: Multiple imputation*

Missing pre-BD/post-BD FEV1 values will be imputed multiple times using a regression model. Imputation will be conducted sequentially as the imputation for each visit will incorporate information from prior visits. Specifically, the covariates to be included are treatment group, gender, baseline height, baseline eosinophil strata, region, background ICS dose level at randomization, baseline value, and change from baseline in FEV1 at all prior visits. Forty imputations will be performed. For each imputation, the change from baseline in pre-BD/post-BD FEV1 at Week 12 will be analyzed by an ANCOVA model with treatment, gender, height, baseline value, baseline eosinophil strata, region, and background ICS dose level at randomization as covariates. Valid statistical inference will be generated by combining results from these 40 analyses using Rubin's rule.

- *Sensitivity analysis 4: Control-based multiple imputation*

This approach assumes that after treatment discontinuation, patients from the active treatment groups will exhibit the same future evolution as those in the placebo group. The implementation is similar to that of the standard multiple imputation approach above (sensitivity analysis 3), except when fitting the imputation model, only data from the placebo group will be used and treatment will not be included as a covariate.

Technical details are provided in [Appendix H](#).

Subgroup analysis

Subgroup analyses of change from baseline in pre-BD and post-BD FEV1 will be conducted in the same subgroups as defined for the primary endpoint based on the primary analysis method for the secondary endpoints. Within each subgroup, descriptive statistics including number of patients, mean, standard error, and LS means will be provided for each treatment group. Difference in LS means and the corresponding two-sided 95% CI will be provided for each pairwise treatment comparison.

Treatment-by-subgroup interaction at Week 12 and its p-value will be derived from a MMRM model. The model will include change from baseline in FEV1 values up to week 12 following the rules in [Table 5](#). Treatment, gender, baseline height, baseline eosinophil strata, region, background ICS dose level at randomization, visit, treatment by-visit interaction, baseline value, baseline-by-visit interaction, subgroup (if different from the aforementioned covariates), subgroup-by-treatment interaction and subgroup-by-treatment-by-visit interaction will be the covariates.

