#### **6.1.1 Background therapy (ICS/LABA) withdrawal phase**

Withdrawal of background therapy with the ICS fluticasone and the LABA salmeterol, during the 12-week IMP treatment period, will be performed as described in [Section 8.2.1](#), and summarized below (for overview please refer to [Section 1.1](#) and [Section 1.2](#)).

At Week 4 (Visit 6) post-randomization, the LABA component (salmeterol) will be withdrawn, and patients will be switched from their BID fluticasone/salmeterol combination therapy to a clinically comparable ICS dose of fluticasone BID monotherapy, as approved for region:

- Fluticasone (DPI formulation):  
1 puff of 250 mcg BID or  
2 puffs of 250 mcg (500 mcg) BID,

OR

- Fluticasone (MDI formulation):  
2 puffs of 110 mcg (220 mcg) BID or  
2 puffs of 220 mcg (440 mcg) BID

OR

- Fluticasone (MDI formulation):  
2 puffs of 125 mcg (250 mcg) BID or  
2 puffs of 250 mcg (500 mcg) BID

The ICS component (fluticasone) will be withdrawn by a step-wise dose reduction starting at Week 6 (Visit 8) and will continue at each Weeks 7, 8, and 9 (Visits 9, 10, and 11, respectively), provided that patients do not experience a LOAC event.

An appropriate inhaler for each required ICS dose while patient is in screening and on IMP treatment will be provided by the Sponsor per local regulation.

Patients that meet the criteria for a LOAC, at any time during the randomized IMP treatment phase, will (be):

- Discontinue early from IMP treatment,
- Evaluated and receive treatment by the Investigator with standard of care according to standard medical practice,
- Resume their individual prescreening ICS/LABA background therapy and
- Followed for safety during the 20-week Post IMP Treatment Period.

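### SAP 2.4.4.2 gives two incompatible rules for FEV1 after loss of asthma control: the text drops every later value, while Table 5 keeps the end-of-treatment value for some patients

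*SAP*

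**What the plan says.** SAP 2.4.4.2 sets the data rule for pre- and post-bronchodilator FEV1, the only secondary efficacy endpoints, in two steps.

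- The text: "FEV1 values after a LOAC event or initiation of rescue medication will not be included for primary assessment of the secondary endpoints". Either condition is enough, so a LOAC event alone ends the usable data.
- The following sentence: "Inclusion of change from baseline in FEV1 values in the model will follow the rules in Table 5". Data that Table 5 does not include are set to missing.

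The first row of Table 5 covers LOAC with a footnote-a trigger: a sustained reliever increase, a large ICS increase or systemic steroid. It stops at the last value before the LOAC. The second row, "LOAC without rescue medication", runs to the "value collected at EOT". Footnote b defines that row: "If the patient meets none of the three criteria listed above and meets one or both of the following". The two items listed are a morning PEF fall of at least 30% on two consecutive days, and "Requiring Hospitalization or emergency room visit".

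Under Protocol 6.1.1, patients with LOAC stop study drug and "receive treatment by the Investigator with standard of care according to standard medical practice". Protocol 6.1.2 places their EOT visit as soon as possible after early discontinuation. Protocol 11.4.2.2 leaves the inclusion rule to the SAP, so it offers no tie-break.

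Sensitivity analysis 1 is described as "Inclusion of all FEV1 measurements collected up to EOT for all patients".

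**The concern.** For a patient in the second row, the text discards the EOT value and the table keeps it. This choice decides which values enter the main secondary analysis. It is not neutral between arms, because the planning LOAC rates are 40% on placebo and 14% on SAR440340.

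The same table governs the FEV1 subgroup interaction model (SAP 2.4.4.2), the other continuous endpoints and the ACQ-5 and AQLQ(S) responder analyses (SAP 2.4.4.4.1).

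The second row also does not isolate untreated patients. A patient given a bronchodilator on a single day in an emergency room, with no systemic steroid and no qualifying ICS increase, meets no footnote-a trigger and is classed as not rescued. Any FEV1 measured afterwards may be lowered by the event or raised by its treatment.

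**Working it through.** **The two rules side by side**

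| Type of LOAC | Text of 2.4.4.2 | Table 5 |
|---|---|---|
| Any footnote-a trigger | Drop values after LOAC | Last value before LOAC |
| PEF fall only | Drop values after LOAC | Keep up to EOT |
| Hospital/ER, with or without PEF fall, no footnote-a trigger | Drop values after LOAC | Keep up to EOT |

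The rules agree in the first line and conflict in the other two. Sensitivity analysis 1 is more inclusive than Table 5. None of the four listed sensitivity analyses is defined by dropping everything after LOAC.

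**The plan's own FEV1 figures** (Protocol, Clinical Trial Summary: SD 0.35 L, 50 per group, 5% level taken as two-sided, 80% power for 0.2 L, smallest significant difference 0.14 L)

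- n per group = 2 × (1.96 + 0.8416)² × 0.35² / 0.2² = 48.1, so 49 (stated 50).
- Power with 50 per group = Φ(0.2/0.07 − 1.96) = 81.5%, where 0.07 = 0.35 × √(2/50). With the t distribution it is 80.8%.
- Smallest significant difference = t(0.975, 98) × 0.07 = 0.139 L.

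These reproduce, and the conflict changes none of them.

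**Patients affected** (60 per arm; LOAC rates from Protocol 11.1 and SAP 1.3)

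- Expected LOAC: 60 × 0.40 = 24 on placebo; 60 × 0.14 = 8.4 on SAR440340.
- The share f in the second row is not in the documents. I assume 10% to 50%.
- Affected: 24 × f = 2.4 to 12 on placebo; 8.4 × f = 0.8 to 4.2 on SAR440340.

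**Effect on the crude Week 12 contrast**

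SAP Table 7 assigns values by study day. Only days 82–112 (pre-bronchodilator) or 78–112 (post-bronchodilator) count as Week 12. An EOT value from an earlier LOAC maps to an earlier visit and reaches the Week 12 estimate only indirectly through the repeated-measures model.

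Further assumptions:

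- A share w of 25% to 100% of the affected values falls in the Week 12 window.
- These values differ from the other patients' by g = 0.2 to 0.4 L.
- All patients without LOAC contribute a Week 12 value: 36 on placebo and 51.6 on SAR440340.

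Shift in an arm mean = g × a / (c + a), where a is the number of values kept and c the number of patients without LOAC.

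- Low (f = 0.10, w = 0.25, g = 0.2): placebo 0.2 × 0.6/36.6 = 0.0033; SAR440340 0.2 × 0.21/51.81 = 0.0008; difference 0.002 L.
- Middle (f = 0.25, w = 0.5, g = 0.4): placebo 0.4 × 3.0/39.0 = 0.031; SAR440340 0.4 × 1.05/52.65 = 0.008; difference 0.023 L.
- High (f = 0.50, w = 1, g = 0.4): placebo 0.4 × 12/48 = 0.100; SAR440340 0.4 × 4.2/55.8 = 0.030; difference 0.070 L.

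If the kept values are low, keeping them widens the difference in favour of SAR440340. If treatment has raised them, keeping them narrows it.

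**The case against.** The strongest reply is that the SAP itself says which rule operates. The model follows Table 5, and later analyses refer to the table again. That stands. A reader might infer two competing analysis datasets, but the documents define only one. A programmer would probably build it from Table 5, and the conflict lies between two instructions.

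A reader might also infer that hospitalised and emergency-room patients in general keep their later FEV1. They do not. Anyone who also has a reliever, ICS or systemic-steroid trigger falls in the first row. The remaining hospital/ER group is probably small, and PEF-only LOAC may make up most of the second row.

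There is also a plausible reason for keeping PEF-only cases. Background controller is resumed at the EOT visit, that visit comes quickly, and spirometry requires at least 6 hours without reliever. The value may therefore precede most treatment. But nothing in the protocol requires this order, and the argument is weakest for a patient already treated in hospital.

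SAP 1.5 gives the intent behind moving these rules into the SAP: EOT data after LOAC could be confounded by medication given after the event. That intent supports a cautious rule for hospital/ER cases. It does not by itself rule out PEF-only cases.

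Finally, this is a secondary endpoint in a Phase 2a study with nominal p-values. That limits the consequence, but the main FEV1 dataset still needs one definition.

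**Conclusion.** The contradiction is real and can be shown from SAP 2.4.4.2 alone. Table 5 is the likely operative rule, but the text bars values that the table keeps, and no listed analysis would show the effect of choosing one over the other. Classing hospital/ER LOAC as not rescued when no footnote-a trigger is met is hard to square with the protocol's treatment of all LOAC patients.

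The size is uncertain: about 2–12 of 60 placebo and 1–4 of 60 SAR440340 patients, and a crude shift of about 0.002–0.07 L in an unknown direction. At its top the range is half the stated 0.14 L threshold, and it gets there only if every assumption takes its extreme value together. The second-row share, the window share and the FEV1 gap are all assumptions, and the shift is a difference in simple means, not a simulation of the repeated-measures model. The hospital/ER part alone cannot be estimated.

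A reader might assume a 0.5 L gap and 25–50% of LOAC in the second row, and compute (0.40 − 0.14) × 0.25 to 0.50 × 0.5 = 0.033 to 0.065 L. The documents do not support that as a floor. The 0.5 L has no source, equals 1.4 times the planning SD (0.5/0.35), and the calculation counts every affected value at Week 12 regardless of the Table 7 windows.

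**What to change.** Before unblinding, amend SAP 2.4.4.2 so that the sentence and Table 5 state the same rule:

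- For data inclusion only, treat hospital/ER LOAC like the first row and use the last value before LOAC.
- If PEF-only LOAC stays in the second row, reword the sentence to say that EOT values are kept for those patients.
- Add a sensitivity run of the same repeated-measures model that drops all FEV1 values after any LOAC. Sensitivity analysis 1 covers only the opposite rule.

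The cost is SAP wording, one derivation flag and one model rerun. No new data are needed, since the rule depends on the type of LOAC and not on the clock time of treatment relative to spirometry.
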